## 2.3 EXPLORATORY OBJECTIVES AND ASSOCIATED ENDPOINTS

Exploratory Objectives	Associated Exploratory Endpoints
1. Describe the efficacy of VGX-3100, administered alone or in combination with imiquimod, at Week 74 and/or Week 96 as measured by reduction in the surface area of the qualifying  vulvar lesion(s), in subjects without a complete resolution at Week 48	1. Percent reduction in the cumulative surface area of the acetowhite vulvar lesion(s) as determined by the quantitative analysis of standardized pre-biopsy photographic imaging of the qualifying  lesion (s) at Week 74 and/or Week 96 compared to baseline  . Results will be classified as: no clinically significant lesion resolution (reduction in lesion area of 0-25%), partial lesion area resolution (>25% and <100% reduction), and complete lesion resolution (no visible lesion).
2. Describe the efficacy of 5 or 6 doses of VGX-3100, alone or in combination with prior imiquimod, as measured by histologic regression of vulvar HSIL	2. Proportion of subjects with no evidence of vulvar HSIL on histology (i.e. biopsies or excisional treatment) at Week 74 for subjects who receive 5 doses of VGX-3100 and at Week 96 for subjects who receive 6 doses of VGX-3100.
3. Describe the efficacy of 5 or 6 doses of VGX-3100, alone or in combination with prior imiquimod, as measured by virologic clearance of HPV-16/18	3. Proportion of subjects with no evidence of HPV-16/18 in vulvar tissue samples at Week 74 and/or Week 96.
4. Evaluate tissue immune responses to VGX-3100, and VGX-3100 with imiquimod, as measured in vulvar tissue samples	4. Assessment of pro-inflammatory and immunosuppressive elements in tissue 
5. Describe virologic clearance of HPV-16/18 from non-vulvar anatomic locations	5. Proportion of subjects who have cleared HPV-16/18 on specimens from non-vulvar anatomic locations without surgical intervention (inclusive of cervix, oropharynx, vagina and intra-anus) at Week 48 compared to baseline
6. Characterize HLA haplotypes and the correlation with efficacy	6. Proportion of subjects with regression of HSIL on histology (i.e. biopsies or excisional treatment) at Week 48 visit
7. Describe association of microRNA (miRNA) profile, previous vulvoscopy, and HPV testing results with Week 48 histologic regression	7. Vulvoscopy, HPV test results (vulvar swab and vulvar tissue) and miRNA profile (Day 0, Week 15 and 48) in conjunction with histologic regression of vulvar HSIL at Week 48 visit
8. Describe patient reported outcomes (PRO) for subjects treated with VGX-3100 and VGX-3100 with imiquimod	8. PRO endpoints will be obtained at Day 0 prior to first dose, Weeks 4, 12, 24 after dosing, and at Weeks 15, 27, 48, 52, 74, 96 and 100.

### 3. STUDY DESIGN

HPV-201 is a Phase 2, randomized, open-label efficacy study of VGX-3100 (DNA plasmids encoding E6 and E7 proteins of HPV types 16 and 18) administered by IM injection followed by EP delivered with CELLECTRA™ 2000 alone or in combination with imiquimod in adult women with histologically confirmed vulvar HSIL associated with HPV-16/18. Approximately 36 subjects will be enrolled. Twenty-four subjects will receive VGX-3100 alone and 12 subjects will receive VGX-3100 and topical imiquimod treatment. The Version 3.0 protocol amendment halts enrollment of the VGX-3100 with topical imiquimod study group. All subjects who have already been enrolled into the VGX-3100 with imiquimod study group will continue with all study visits per protocol, but no further participants will be enrolled into this group.

Subjects are randomized in a stratified manner according to (a) recurrent disease at screening (0 vs. 1 or more recurrences), (b) multifocal disease (1 vs. 2 or more lesions at screening), (c) Body Mass Index (BMI) category ( $\leq 25$  vs.  $> 25$  kg/m^2), and (d) age category ( $< 45$  years vs.  $\geq 45$  years).

To be eligible for the study, subjects must sign consent to participate and have a vulvar punch biopsy/biopsies of approximately 4 mm with lesion remaining, and photographs of the acetowhite vulvar lesion(s) at the time of screening. In the case of multifocal disease, the two lesions that potentially contain the most advanced disease, as judged by the Investigator, should be chosen for biopsy using vulvoscopy and documented using standardized high resolution photography with a digital single-lens reflex (SLR) camera on the case report form. Biopsy slides will be sent to a PAC for evaluation prior to enrollment. In order to be eligible for enrollment, the PAC must assign the diagnosis of vulvar HSIL based on the biopsy sample(s). Subjects must also have a vulvar specimen test positive for HPV genotype 16 and/or 18 to be eligible for participation in the study.

To assess quality of life and related impacts on subjects, PRO instruments will be provided and will include the Short Form Health Survey version 2 (SF-36v2™), the EQ-5D-5L (EuroQol Research Foundation), WOMAN-PRO (WOMen with vulvar Neoplasia) Clinical Trial Version 2.0 and two additional PRO questions assessing quality of life after surgery or biopsy.

The total duration of the study is up to 10 weeks for the screening period and 100 weeks for the treatment and follow-up periods.

#### 3.1 TREATMENT REGIMENS

All eligible subjects who consent to participate in the study will receive four doses of 6 mg of VGX-3100 administered by IM injection followed by EP. The first dose will be administered as soon as possible following confirmation of the HSIL diagnosis, HPV-16/18 status and all other eligibility criteria but no more than 10 weeks following collection of the subject's biopsy specimen used for diagnosis by the PAC.

Each dose of VGX-3100 will be administered in a 1 mL volume IM (deltoid preferred site, or the anterolateral quadriceps as an alternate site) followed immediately by EP with the CELLECTRA™ 2000 device. As shown in [Figure 1](#), study subjects will receive at least 4 doses of VGX-3100 and potentially a 5th and 6th dose depending upon their disposition with regard to histologic and lesion area changes. The first dose will be administered on Day 0, the second at Week 4, the third at Week 12, and the fourth dose will be administered at Week 24. Subjects with no HSIL at Week 48 (Subgroups A and B) will

receive 4 doses. Subjects with HSIL at Week 48, who have a reduction in lesion size or no increase in lesion size from baseline (Subgroups C or D), may receive a fifth dose at Week 52 per the judgment of the Investigator. Subjects with HSIL at Week 74, who have a reduction in lesion size or no increase in lesion size from baseline (Subgroups C or D), may receive a sixth dose at Week 78 per the judgment of the Investigator. Subjects in Subgroup E should receive surgical treatment per the judgment of the Investigator. All subjects will complete the study at Week 100.

Imiquimod treatment – Participants who have been enrolled in the VGX-3100 with imiquimod study group will continue with study visits per protocol, but no further participants will be enrolled into this study group. Subjects randomized to the VGX-3100 with imiquimod study group will apply imiquimod 5% cream to the vulvar lesion beginning in the evening on Day 0, and will continue to apply treatment three times per week for 20 weeks (inclusive of administration in the evening of VGX-3100 dosing). Subjects unable to tolerate imiquimod treatment may reduce their dosing frequency, and will document their use on the imiquimod dosing log provided.

### 3.2 EFFICACY ASSESSMENT

The efficacy assessment will be based upon histopathology. Visualization of a normal appearing vulva by visual inspection with vulvoscopy is insufficient evidence to confirm disease regression. Disease regression will be based on histopathologic assessment at Week 48, 74 and 96. Subjects will be monitored during the course of the study by vulvoscopy. Lesion(s), defined as areas that stain acetowhite, will be assessed during vulvoscopy at Screening, Day 0, and Weeks 4, 12, 27, 48, 74 and 96 visits. Using standardized high resolution digital photographic imaging, vulvar lesion(s) will also be quantitatively measured at Screening, Day 0, and Weeks 4, 12, 27, 48, 74 and 96.

Biopsies obtained as part of the study at Screening will be from the region of most advanced disease as judged by the Investigator, and must be approximately 4 mm in length. Visible lesion must remain after screening biopsy to ensure measurement on study.

The decision process following results of the Week 48 biopsy are described in [Figure 2](#) and are as follows: At Week 48, the subject will undergo repeat vulvar punch biopsy/biopsies of the qualifying lesion as study start from the region of potentially most advanced disease based upon the judgment of the Investigator (see [Table 2](#) for Minimally Required Biopsy Procedures). If after evaluation of biopsy tissue by the PAC there is no evidence of HSIL ([Figure 2](#), Subgroups A or B), the subject will continue to Week 74 for vulvoscopy, and biopsy of the same qualifying lesion as study start from the region of potentially most advanced disease based upon the judgment of the Investigator.

If after evaluation of the biopsy tissue HSIL remains, but there is a reduction in lesion size or no increase in lesion size from baseline ([Figure 2](#), Subgroups C or D), the Investigator has the option to give the subject a 5th dose of VGX-3100 at Week 52, and the subject will continue on study with vulvoscopy and biopsy at Week 74. Alternatively, the Investigator may choose to treat the subject with surgical or standard treatment, and the subject will continue on study without further biopsy.

The decision process following results of the Week 74 biopsy are described in [Figure 3](#) and are as follows: At Week 74, the subject will undergo repeat vulvar punch biopsy/biopsies of the same lesion as at study start Investigator(see [Table 2](#)). If after

evaluation of biopsy tissue by the PAC there is no evidence of HSIL (Subgroups A or B), the subject will continue to Week 96 for vulvoscopy and biopsy of the same lesion as at study start. Investigator If HSIL remains but there is a reduction in lesion size or no increase in lesion size from baseline (Subgroups C or D), the Investigator has the option to give the subject a 6th dose of VGX-3100 at Week 78, and the subject will continue on study with vulvoscopy and biopsy at Week 96. Alternatively, the Investigator may choose to treat the subject with surgical or standard treatment, and the subject will continue on study without further biopsy.

The decision process following results of the Week 74 biopsy are as described in [Figure 4](#) and are as follows: At Week 96, the subject will undergo repeat vulvar punch biopsy/biopsies of the same lesion as study start, but from the region of potentially most advanced disease based upon the judgment of the Investigator. (see [Table 2](#)). If there is no vulvar HSIL (Subgroups A or B), no further procedures are required. If after evaluation of biopsy tissue by the PAC there is vulvar HSIL (Subgroups C or D), or worsening disease (Subgroup E), the subject will receive surgical or other standard treatment.

In the event of worsening disease (i.e., Subgroup E - any increase in lesion area from baseline or worsening to cancer), the subject will receive surgical treatment per the Investigator's judgment and will continue on study through Week 100 with vulvoscopy, but without further study treatment or biopsy. For a finding of carcinoma, subjects will receive surgical treatment, and be discontinued from study treatment. The event will be reported as an SAE per [section 7.1.4](#). If wide excision is required, the sample obtained will be sent to the PAC for evaluation.

Pre-biopsy Vulvoscopy Finding	Minimally required procedure
No acetowhite lesion	Vulvar punch biopsy and lesion photography; biopsy should be conducted of the same qualifying lesion as study entry from the region of potentially most advanced disease based upon judgment of the Investigator.
Acetowhite Lesion	Vulvar punch biopsy and lesion photography; biopsy should be conducted of the same qualifying lesion as study entry from the region of potentially most advanced disease based upon judgment of the Investigator.
Multiple acetowhite lesions	Vulvar punch biopsies and lesion photography; biopsy should be conducted of the same qualifying lesions as study entry from the region of potentially most advanced disease based upon judgment of the Investigator.

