### 3.2 EFFICACY ASSESSMENT

The efficacy assessment will be based upon histopathology. Visualization of a normal appearing vulva by visual inspection with vulvoscopy is insufficient evidence to confirm disease regression. Disease regression will be based on histopathologic assessment at Week 48, 74, and at Week 96 for subjects reaching Week 96 prior to Amendment 5.0 or for whom that is the final visit. Subjects will be monitored during the course of the study by vulvoscopy. Lesion(s), defined as areas that stain acetowhite, will be assessed and photographed during vulvoscopy at Screening, Day 0, and Weeks 4, 12, 27, 48, 74, and at Week 96 for subjects who have reached this timepoint prior to Amendment 5.0 or for whom this is the final visit. Using standardized high resolution digital photographic imaging, vulvar lesion(s) will also be quantitatively measured at Screening, Day 0, and Weeks 48, 74, and at Week 96 for subjects who have reached that timepoint prior to Amendment 5.0 or for whom that is their final visit.

Biopsies obtained as part of the study at Screening will be from the region of most advanced disease as judged by the Investigator, and must be approximately 4 mm in

length. Visible lesion must remain after screening biopsy to ensure measurement on study. A qualifying lesion is defined as a vulvar lesion which is confirmed to be HPV-16 and/or HPV-18 positive and have histologically confirmed vulvar HSIL by the PAC at screening.

The decision process following results of the Week 48 biopsy are described in [Figure 2](#) and are as follows: At Week 48, the subject will undergo repeat vulvar punch biopsy/biopsies of the same lesions as study start, from the region of most advanced disease based upon the judgment of the Investigator (see [Table 2](#) for Minimally Required Biopsy Procedures).

If after evaluation of biopsy tissue by the PAC there is no evidence of HSIL ([Figure 2](#), Subgroups A or B), the subject will continue to Week 74 for vulvoscopy, and biopsy of the same lesion(s) as study start.

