In the event of worsening disease prior to the end of the study (i.e., Subgroup E), the subject will receive surgical treatment per the Investigator's judgment and will continue on study with vulvoscopy, but without further study treatment or biopsy. In the event of worsening disease at the final visit, the subject will receive standard of care treatment (not part of study activities) per their treating physician. If wide excision is conducted at or prior to the subjects last on site visit, the sample obtained will be sent to the PAC for evaluation. For a finding of carcinoma, subjects will receive surgical treatment, and be discontinued from study treatment. The event will be reported as an SAE per [section 7.1.4](#).

All visible lesions should be biopsied at Week 48. For subjects for whom Week 78 is their final visit, all visible lesions should be biopsied at Week 74. For subjects for whom the final visit is Week 96, all visible lesions should be biopsied at Week 96.

If there is a new lesion identified at evaluation, or a non-qualifying lesion that is rebiopsied and confirmed to be vulvar HSIL and HPV-16/18 positive at evaluation, a discussion will take place between the Medical Monitor and the Principal Investigator to determine if additional dosing at Week 52 is appropriate.

Pre-biopsy Vulvoscopy Finding	Minimally required procedure
No acetowhite lesion	Vulvar punch biopsy and lesion photography; biopsy should be conducted of the same qualifying lesion as study entry from the region of potentially most advanced disease based upon judgment of the Investigator; new lesions or lesions that did not qualify at baseline should be biopsied at evaluation.
Acetowhite Lesion	Vulvar punch biopsy and lesion photography; biopsy should be conducted of the same qualifying lesion as study entry from the region of potentially most advanced disease based upon judgment of the Investigator; new lesions or lesions that did not qualify at baseline should be biopsied at evaluation
Multiple acetowhite lesions	Vulvar punch biopsies and lesion photography; biopsy should be conducted of the same qualifying lesions as study entry from the region of potentially most advanced disease based upon judgment of the Investigator; new lesions or lesions that did not qualify at baseline should be biopsied at evaluation

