## **6.11 VULVAR HPV TESTING**

At Screening, Weeks 48, 74, and 96, a vulvar punch biopsy sample of approximately 4 mm will be obtained and sent to a central laboratory for HPV genotyping by PCR. Samples will not be obtained at week 96 on subjects who complete the study prior to that timepoint per Amendment 5.0.

In the case of multifocal disease, a vulvar biopsy of approximately 4 mm will be obtained from two lesions that potentially contain the most advanced disease as judged by the Investigator. The subject will be requested to abstain from sexual activity and refrain from use of douching to eliminate potential interference with the results of HPV testing.

The subject will be requested to abstain from sexual activity and refrain from use of douching or vaginal lubricants/medication for a period of 24 hours prior to collection of vulvar punch biopsy to eliminate potential interference with the results of HPV testing.

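### Protocol version 5.0 gives conflicting Week 48 biopsy instructions; under the Table 2 minimum, a woman with two qualifying lesions can be a responder although one was never re-sampled

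*Protocol*

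**What the plan says.** All references are to protocol version 5.0 unless stated.

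**Entry.** In multifocal disease, section 3 says that "the two lesions that potentially contain the most advanced disease, as judged by the Investigator, should be chosen for biopsy using vulvoscopy". A lesion qualifies if the Pathology Adjudication Committee confirms HSIL and it is positive for HPV-16 and/or HPV-18, so a woman can enter with two qualifying lesions.

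**Week 48, narrower wording.**
- Table 2 of section 3.2 chooses its rows by "Pre-biopsy Vulvoscopy Finding". For no acetowhite lesion, and for one, "biopsy should be conducted of the same qualifying lesion as study entry from the region of potentially most advanced disease". For multiple acetowhite lesions, "biopsy should be conducted of the same qualifying lesions as study entry". The same words stand in version 3.0. Version 5.0 added only new lesions and lesions that did not qualify at baseline.
- Section 3.2 also says: "All visible lesions should be biopsied at Week 48".
- The synopsis, under Efficacy Assessment, has the Week 48 biopsy taken from the lesion sampled at study start, in the singular.

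**Week 48, wider wording.**
- The section 3.2 narrative calls for "repeat vulvar punch biopsy/biopsies of the same lesions as study start", and refers to Table 2 for the minimum.
- Section 6.11, which covers Week 48, says that in multifocal disease "a vulvar biopsy of approximately 4 mm will be obtained from two lesions that potentially contain the most advanced disease".
- Footnote l of Table 1 says that all lesions are biopsied at Weeks 48, 74 and 96 as applicable, with no condition on visibility.

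**What counts as response.** Tables 3 to 6 and 8 define a responder by the absence of histologic and/or HPV-16/18 evidence, together with no non-study treatment for vulvar HSIL. None of them requires tissue from every qualifying lesion. Section 3.2 states: "Visualization of a normal appearing vulva by visual inspection with vulvoscopy is insufficient evidence to confirm disease regression".

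**The concern.** The narrower instructions tie the amount of tissue to what can still be seen. A site that follows Table 2 as its floor may leave a qualifying lesion unsampled because it no longer stains. The responder tables ask only whether evidence of disease or virus was found, and a site that was not biopsied yields none. For that lesion, regression and clearance would then rest on appearance, which section 3.2 calls insufficient.

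At stake are the primary endpoint and the regression, clearance, regression-to-normal and regression-or-clearance endpoints. Section 8.9 tests the primary endpoint in each arm against a fixed 2%, and very few responders are needed to succeed.

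**Working it through.** **1. The instructions applied to one case.** Take a woman with two qualifying lesions at entry. The qualifying sites that must be sampled at Week 48 are:

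| Instruction | Both still acetowhite | One still acetowhite | Neither acetowhite |
|---|---|---|---|
| Table 2 minimum | 2 | 1 | 1 |
| Visible-lesions sentence, section 3.2 | 2 | 1 | 0 |
| Synopsis (singular) | 1 as worded | 1 as worded | 1 as worded |
| Narrative, section 3.2 | 2 | 2 | 2 |
| Section 6.11 (two lesions) | 2 | 2 | 2 |
| Table 1, footnote l (all lesions) | 2 | 2 | 2 |

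Two cells need a caveat. Section 6.11 names the two lesions that may hold the most advanced disease, which need not be the two that qualified at entry. Section 3.2 defines lesions as areas that stain acetowhite, so a literal reader could exclude a non-staining site from footnote l and section 6.11. The narrative in section 3.2 is the clearest wider instruction, yet it points to Table 2 for the minimum.

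**2. Direction of the bias.** In each of Tables 3 to 6 and 8, an additional biopsy can add evidence of disease or HPV-16/18 but cannot remove it. Sampling the second lesion can therefore turn a responder into a non-responder, never the reverse. Omitting it can only leave the response rate unchanged or raise it.

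**3. The plan's own figure.** Inputs from sections 8.3 and 8.9: null rate 2%; true rates 20% and 28%; one-sided 0.025; 80% power; 90% evaluable; exact test. The critical value is the smallest r with P(X ≥ r | n, 0.02) < 0.025.
- VGX-3100 alone: the smallest n with at least 80% power is 21 (r = 3, power 0.821; n = 20 gives 0.794). 21/0.9 = 23.3, so 24.
- Combination: n = 10 (r = 2, power 0.817; n = 9 gives 0.766). 10/0.9 = 11.1, so 12.
- Total 24 + 12 = 36, as stated. This point does not dispute that figure.

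**4. What one woman is worth.** Exact one-sided p against 2%:
- 2/21: 1 − 0.98^21 − 21(0.02)(0.98^20) = 1 − 0.6543 − 0.2804 = 0.065. Fails.
- 3/21: 0.0653 − 210(0.02^2)(0.98^19) = 0.0653 − 0.0572 = 0.008. Succeeds.
- 1/10: 1 − 0.98^10 = 0.183. Fails.
- 2/10: 0.1829 − 10(0.02)(0.98^9) = 0.1829 − 0.1667 = 0.016. Succeeds.

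In either arm, a single woman classified as a responder with an unsampled lesion can carry the result across the threshold.

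**The case against.** The strongest reply is that Table 2 is a floor and the protocol asks for more elsewhere. The section 3.2 narrative, section 6.11 and footnote l all point to sampling beyond one lesion, and a site reading the whole document would not stop at one punch. The protocol also uses the singular loosely, at times pairing biopsies in the plural with one lesion. This stands to the extent that a reader should not infer that one punch is the protocol's settled rule. What remains is a contradiction: the wider text itself refers to Table 2 for the minimum, and version 5.0 added a sentence limited to visible lesions.

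Second, a reader might infer that women are judged on appearance alone. They are not: Table 2 requires a biopsy of a qualifying lesion even when nothing is visible. Only a second, unsampled lesion is affected.

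Third, no passage says that an unsampled lesion is scored as cleared. Section 8.4 limits the mITT population to women with the endpoint of interest, section 8.13 rules out imputation, and section 8.9 analyses the binary endpoints on qualifying and new lesions and again on all lesions. Such a woman could be treated as non-evaluable, and the SAP, not shown here, may settle this. It is fair not to call the combination rule missing. But the responder tables as written would admit her, and a rule in the SAP would not supply the tissue.

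Fourth, one could assume a probability of residual disease at the unseen site and turn it into a factor of overstatement. The protocol does not support that. It gives no such probability, the two sites in one woman need not be independent, and section 1.1.17 describes the response as systemic. Multifocality is a stratification factor, but it counts lesions, not qualifying lesions, so it does not size the group.

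**Conclusion.** The point holds as a contradiction in how the primary endpoint is ascertained. Table 2, the visible-lesions sentence and the synopsis allow fewer biopsies than the section 3.2 narrative, section 6.11 and footnote l. Under the narrower set, a woman with two qualifying lesions can be classed as a responder on one negative punch.

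The direction is certain: any resulting error favours response. The size is not known. It depends on how many women had two qualifying lesions, how often one or both stopped staining, how often sites sampled only the minimum, and how often the unsampled site still held HSIL or HPV-16/18; the protocol gives none of these. The success thresholds show why even one case matters: p moves from 0.065 to 0.008 between 2/21 and 3/21, and from 0.183 to 0.016 between 1/10 and 2/10. These denominators are the smallest evaluable numbers that give the planned power, not observed counts. The matter should be corrected, but it does not show that the response rate is in fact overstated.

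**What to change.** 1. Reconcile Table 2, the visible-lesions sentence and the synopsis with the section 3.2 narrative, section 6.11 and footnote l. Key the rows of Table 2 to the qualifying lesions at entry, whether or not they are still visible. This asks for no biopsy beyond what the narrative already calls for.
2. List every responder who lacks Week 48 tissue from any qualifying lesion. This also covers women already past Week 48, whose sampling can no longer be changed.
3. Add a sensitivity analysis of the primary, regression and clearance endpoints that counts those women as non-responders. Leave the primary responder definition as it stands: changing it once Week 48 results exist in an open-label trial would raise its own questions.

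The cost is a wording change, one listing and one additional analysis. The downside is that the response rate in that analysis may be lower.
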